1. Measure and compare the change in interstitial fibrosis (morphometric analysis of trichrome stained slides) at one-year post-transplant in patients converted to everolimus, low intensity tacrolimus and prednisone versus the standard of care tacrolimus, mycophenolate and prednisone regimen.

Secondary objectives:

1. Measure and compare the estimated GFR (using the 4-variable modified MDRD equation) in patients converted to everolimus, low intensity tacrolimus and prednisone versus the standard of care tacrolimus, mycophenolate and prednisone regimen, both at one year and two years post-transplant.
2. Compare the patient and graft survival rates at one-year post-transplant in each group.
3. Measure and compare the rates of immunosuppressant discontinuation and modification for each group.
4. Measure and compare the incidence of significant immunosuppressant-related adverse drug reactions for each group.
5. Compare the rates of post-transplant infections, including CMV, BK, and admissions to the hospital for infectious causes in each group.

Endpoints 6 through 10 are exploratory:

6. Measure and compare the rates and quantity of *de novo* donor specific antibody formation at one-year post-transplant in each group; this will address the important clinical question of the risk of humorally mediated alloimmune events with CNI minimization.
7. Determine the impact of gene variants for donor APOL1, donor ABCB1, recipient cytochrome P450 3A5, and donor and recipient angiotensin receptor and angiotensin converting enzyme on the primary objectives. This endpoint addresses pathways that could potentially impact outcome but are not measured by traditional risk factors and explanatory variables such as rejection and immunosuppressant concentrations.
8. Examine changes in gene expression and urinary proteomics using high throughput methods on peripheral blood, renal biopsy tissue and urine. The rationale underlying this endpoint is that these markers could yield potential biomarkers that may be used as a companion diagnostic aid in selecting patients at particularly high risk for renal progression or CNI nephrotoxicity.

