Applanation tonometry will be performed by placing a micromanometer-tipped probe against the skin surface over the artery of interest and obtaining pressure waveforms transmitted through the skin surface. Pressure waveforms will be recorded during an 8-second period using a high-fidelity SPC-301 micromanometer (Millar Instrument, Inc., Houston, TX, USA) interfaced with a computer employing SphygmoCor, version 9.0 software (AtCor Medical Pty. Ltd., West Ryde, New South Wales, Australia). To determine aortic BP, the pulse wave obtained from radial tonometer recordings will be calibrated by manual measurement (auscultation) of brachial BP taken immediately before the recordings. The radial pressure waveform will be converted into a central (aortic) waveform using a validated generalized transfer function (GTF) incorporated in SphygmoCor software. Central aortic systolic and diastolic BP will be derived from the aortic waveform and PPc will be calculated from the difference.

Safety Assessment Definitions:

A. Renal Function:

Renal function will be calculated by the eGFR using the 4-variable MDRD formula. Time points for calculations are delineated in the Study Evaluation Schedule located in the Appendix at the end of this protocol. The primary renal function assessments utilized for safety and efficacy analyses will be the eGFR at baseline (randomization) and at 12 months post-transplant.

B. Physical Examination:

A thorough physical assessment will be performed at screening/randomization and at months 3, 4, 6 and 12 post-transplant. Significant findings that are present prior to the start of the study will be included in the Relevant Medical History/Current Medical Conditions on the CRF. Significant findings made after the start of study medication which meet the definition of an AE will be recorded in the AE CRF.

C. Vital Signs:

Vital signs (radial pulse rate and blood pressure) will be recorded as indicated in the Study Evaluation Schedule located in the Appendix at the end of this protocol. Blood pressure and pulse rate will be assessed at the same arm each time of determination and after the subject has rested in the sitting position (may be supine if during hospitalization) for at least five minutes. Measurements will be recorded on the CRF.

D. Height and Weight:

Height and weight will be measured and recorded at screening and during follow-up visits when physical exams are performed. Results will be recorded on the CRF.

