Categorical data will be evaluated based on Fisher's Exact and Chi Square tests where appropriate; descriptive statistics will be used for continuous variables to describe the two patient populations and primary outcomes in each group (% change in interstitial fibrosis and eGFR from month 3 to month 12). Student's T-test or comparable non-parametric tests (such as the Wilcoxon Rank Sum test) will be used to compare the groups for these continuous variables. Patients will be analyzed based on an intent-to-treat basis, except when prohibited by lack of follow-up 12 month biopsies. Kaplan-Meier curves with the log rank test will be used to compare patient and graft survival, acute rejection free survival, and *de novo* donor specific antibody free survival. A p-value of <0.05 will be considered statistically significant. Slope change of eGFR from 3 months to 12 months post-transplant will be calculated and compared as well.

For the genomic comparisons, patients will be grouped based on the presence or absence of known single nucleotide polymorphisms and compared for primary outcomes. If significant baseline differences are noted between groups, multivariate analysis will be conducted to control for these differences. Similar analyses will be conducted for change in mRNA expression and change in urinary proteomic excretion between month 3 and month 12.

This will be an intent-to-treat analysis with all patients undergoing randomization included in the final data analysis, even if removed from study or control medication. Patients screened and consented, but not randomized will be tracked for reasons of non-randomization, but will not be followed for clinical outcomes or included in the final analysis. These patients will be

replaced to insure a total of 60 patients (30 in each group) are randomized and followed to meet study power and sample-size.

Sample size and power: A total of 60 patients, 30 *randomized* in each arm, will provide 89% power (alpha=0.05, two-sided) to detect a significant difference in the percent change in the quantity of interstitial fibrosis between groups when comparing the three month and 12-month protocol biopsies. These calculations used the following assumptions: 10% drop out rate for each group (27 patients in each group will have baseline and follow-up biopsies), with a $64\pm41\%$ change in degree of fibrosis in the control arm and a $13\pm71\%$ change in fibrosis in the investigational arm.

Evaluation schedule:

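### The eGFR comparison differs between the objective and the statistical section, has no named main analysis, and does not prespecify adjustment for eGFR at randomisation

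*Combined protocol and SAP*

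**What the plan says.** Four places in the combined protocol and SAP bear on the eGFR comparison.

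- **Objectives, secondary objective 1:** "Measure and compare the estimated GFR (using the 4-variable modified MDRD equation) in patients converted to everolimus" with the control regimen, "both at one year and two years post-transplant". This is a comparison of eGFR levels, and it is classed as secondary.
- **Safety Assessment Definitions, A. Renal Function:** "The primary renal function assessments utilized for safety and efficacy analyses will be the eGFR at baseline (randomization) and at 12 months post-transplant".
- **Statistical analysis, first paragraph:** the continuous outcomes are described as "primary outcomes in each group (% change in interstitial fibrosis and eGFR from month 3 to month 12", so eGFR is placed among the primary outcomes. The test is given as "Student's T-test or comparable non-parametric tests (such as the Wilcoxon Rank Sum test) will be used to compare the groups for these continuous variables". The paragraph then adds: "Slope change of eGFR from 3 months to 12 months post-transplant will be calculated and compared as well". The error rule is "A p-value of <0.05 will be considered statistically significant".
- **Statistical analysis, second paragraph, after the genomic comparisons:** "If significant baseline differences are noted between groups, multivariate analysis will be conducted to control for these differences".

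No test of the one-year or two-year eGFR level is specified, and no eGFR analysis is named as the main one. The Sample size and power paragraph covers fibrosis only.

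**The concern.** Improvement in GFR is half of the hypothesis stated at the end of the rationale, so this is the trial's main function result. As written, the objective asks for a difference in level, while the analysis delivers a change and a slope. With no main analysis named, the team could obtain significance on one version and not on the other, and nothing in the plan says which result stands.

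Precision is also at stake. eGFR at randomisation is measured in every patient and predicts eGFR at month 12. In the planned tests it enters only as a subtracted value, a divisor or a slope end point, never as a prespecified covariate. With 30 patients per arm, the lost power matters.

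**Working it through.** **1. The plan's own figure.** The only stated power is 89% for fibrosis, with 64±41% against 13±71% and 27 evaluable per arm. The pooled SD is √((41² + 71²)/2) = 57.97. The standard error is 57.97 × √(2/27) = 15.78, and 51/15.78 = 3.23. The noncentral t with 52 df gives 88.7%, so the figure reproduces. It says nothing about eGFR.

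**2. Inputs for eGFR.** From the documents: 30 per arm; two-sided 0.05 (stated for the fibrosis calculation); eGFR at months 3, 6 and 12 (Graft function assessment; Evaluation schedule). Assumed, because the documents give none of them: mean 55, SD 15 and true gain 7 mL/min at month 12, half of it present at month 6; equal correlation ρ between visits of 0.6, 0.7 or 0.8.

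**3. Standard errors of the arm difference.** Let s = 15 × √(2/30) = 3.87.

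- Unadjusted month-12 level: s = 3.87 at any ρ.
- Simple change: s × √(2(1−ρ)). At ρ = 0.7, 3.87 × 0.775 = 3.00.
- Month-12 eGFR adjusted for baseline (ANCOVA): s × √(1−ρ²). At ρ = 0.7, 3.87 × 0.714 = 2.77.
- Least-squares slope on months 3, 6 and 12: the deviations from the mean time are −4, −1 and 5, with sum of squares 42, so the SE is s × √((1−ρ)/42). At ρ = 0.7 it is 0.327. The expected slope difference is (−1 × 3.5 + 5 × 7)/42 = 0.75 mL/min per month.

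**4. Power.** Simulated, because % change has no simple closed form; for the other three rows the formulas above agree to within about one point.

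| Analysis | ρ = 0.6 | ρ = 0.7 | ρ = 0.8 |
|---|---|---|---|
| Month-12 eGFR adjusted for baseline | 60% | 70% | 84% |
| Simple change | 51% | 64% | 80% |
| Slope | 49% | 62% | 79% |
| % change, t-test | 40% | 52% | 69% |

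With 27 per arm the adjusted analysis has about 55/65/80% and % change about 37/48/65%, so the order is unchanged.

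**5. How far this depends on the assumptions.**

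- The variance of simple change relative to ANCOVA is 2(1−ρ)/(1−ρ²) = 2/(1+ρ). This is 1.33, 1.18, 1.11 and 1.05 at ρ = 0.5, 0.7, 0.8 and 0.9.
- Slope power depends on when the effect appears: 53/65/82% if it accrues linearly, and 41/52/69% if it is all present by month 6.

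**6. False positives with no true effect.** % change or slope: 6.6–6.8%. Simple change or slope: 6.0%. Adding a test of the month-12 level: about 11%. One prespecified analysis: 5%.

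**7. Disagreement between the two named analyses.** Take 30 per arm, ρ = 0.7 and a true effect of 0.53 SD, at which the adjusted analysis has about 80% power. With an SD of 25% of the mean, % change is significant in 62.5% of trials, slope in 71.4%, and at least one in 74.1%. Exactly one is therefore significant in 2 × 74.1 − 62.5 − 71.4 = 14.3%. With an SD of 33% of the mean, the same sum is 2 × 75.4 − 57.1 − 72.8 = 20.9%.

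**The case against.** Several points on the other side stand.

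- **Some adjustment is provided for.** A reader might infer that the plan never adjusts for baseline. The conditional multivariate clause rules that out. It is a weak remedy, because it depends on a significant baseline difference, does not name eGFR and may apply only to genotype groups.
- **Error inflation is modest.** A reader might infer that the false-positive rate roughly doubles, to about 11%. That needs a test of the one-year level, which the statistical section does not name. The two analyses it does name are highly correlated and give about 7%. The open choice between t-test and Wilcoxon adds a little.
- **Leaving the level is not what costs power.** Once ρ exceeds 0.5, an unadjusted month-12 level is less precise than a simple change. The loss comes from the missing covariate.
- **The % reading is not the only one.** The phrase can mean % change in fibrosis and plain change in eGFR. The loss against ANCOVA is then 4 to 9 points rather than 15 to 20. A Wilcoxon test would also limit the influence of patients with low starting values on a % change.
- **The Renal Function section does not conflict with a change analysis.** It names the two time points that a month 3 to month 12 change uses.

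None of this supplies a main eGFR analysis or a prespecified baseline covariate.

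**Conclusion.** The concern holds in limited form. The objective and the statistical section define the eGFR comparison differently, no main analysis is named, and adjustment for eGFR at randomisation is not prespecified. Under the assumed values, the adjusted analysis gains 15 to 20 points of power over % change, 4 to 9 over simple change and 5 to 11 over slope with half of the effect present at month 6. Across effect timings the slope loss runs from about 2 to 19 points. These sizes rest on an SD, gain and correlation that the documents do not give; the adjusted analysis had the highest power of the single analyses at every correlation tried.

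The excess of false positives is about 2 points for the two named analyses, so the ambiguity and the lost precision are the stronger grounds for a change. The fibrosis comparison and its 89% power are not affected.

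Two related inconsistencies belong with this point. eGFR is secondary in the Objectives but sits among the primary outcomes in the Statistical analysis section. The two-year comparison has no scheduled visit: Study duration gives 12 months of follow-up and the Evaluation schedule ends at month 12.

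**What to change.** In the Statistical analysis section, state one main eGFR analysis: month-12 eGFR regressed on arm and on eGFR at randomisation, reporting the arm difference in mL/min/1.73 m² with its 95% confidence interval. Label the month 3 to month 12 change and the slope as supportive, and say whether the change is a percentage or a difference in mL/min/1.73 m².

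Then align the Objectives, the Renal Function section and the Statistical analysis section. State once whether eGFR is primary or secondary, and either schedule a two-year eGFR with an analysis or remove the two-year comparison from the objective.

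The analysis change costs wording only, since both eGFR values are already collected. Only keeping the two-year comparison would need further data.

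### The primary fibrosis comparison may use a t-test or a non-parametric test with no rule for choosing, and month-3 fibrosis is not a planned covariate

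*Combined protocol and SAP*

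**What the plan says.** The Primary objectives section states the aim without a scale: "Measure and compare the change in interstitial fibrosis (morphometric analysis of trichrome stained slides) at one-year post-transplant". The Statistical analysis section supplies one, listing "primary outcomes in each group (% change in interstitial fibrosis and eGFR from month 3 to month 12" among the outcomes to be described. For these continuous variables it then says "Student's T-test or comparable non-parametric tests (such as the Wilcoxon Rank Sum test) will be used to compare the groups". It gives no criterion for moving from one test to the other and does not say which is primary. The Wilcoxon test appears only as an example, so even the alternative is not fixed.

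The plan contains one sentence on covariate adjustment: "If significant baseline differences are noted between groups, multivariate analysis will be conducted to control for these differences". It comes directly after the description of the genotype comparisons and names no covariate.

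The Sample size and power paragraph says that 30 randomized per arm "will provide 89% power (alpha=0.05, two-sided") "to detect a significant difference in the percent change in the quantity of interstitial fibrosis between groups". It allows for 10% drop-out, so that "27 patients in each group will have baseline and follow-up biopsies". The assumed percent changes are 64±41 (control) and 13±71 (investigational).

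**The concern.** On the endpoint that sizes the trial, two tests are allowed and nothing says which one counts. This is more than a formality because the plan itself expects unequal spread. Student's t-test compares mean percent change, which is the quantity in the power statement. Wilcoxon responds to any tendency for values in one arm to exceed those in the other. With unequal SDs and skewed data it can reject when the means are equal. Some skew is plausible: percent change cannot fall below -100%, yet a normal distribution with mean 13 and SD 71 puts 5.6% of patients there. The trial is also open label, so the choice should be closed before anyone sees outcome data.

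The second part is efficiency. An evaluable patient is one with both biopsies, so month-3 fibrosis is known for everyone in the comparison. It forms the denominator of the outcome, but no analysis is committed to using it as a covariate.

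**Working it through.** **Inputs from the plan:** 27 evaluable per arm; means 64 and 13; SDs 41 and 71; two-sided alpha 0.05; stated power 89%.

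**Assumptions not in the plan:** the shape of the percent-change distribution (normal; or gamma or lognormal for the month-12/month-3 ratio, matched to the plan's means and SDs), and the correlation r between percent change and month-3 fibrosis.

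**1. Reproduce the stated power.**
- Difference = 64 - 13 = 51.
- SD = sqrt((41² + 71²)/2) = sqrt((1681 + 5041)/2) = sqrt(3361) = 57.97.
- d = 51/57.97 = 0.880; noncentrality = 0.880 × sqrt(27/2) = 3.23.
- Two-sided t-test, 52 df: power 88.7% (Welch 88.4%).

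The stated 89% is the unadjusted t-test on 27 per arm.

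**2. The two tests under the planned effect** (simulation, at least 20,000 trials per setting)

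| Shape | t power | Wilcoxon power | Tests disagree |
|---|---|---|---|
| Normal | 88.7% | 86.1% | 5.5% |
| Gamma | 85.5% | 94.2% | about 9% |
| Lognormal | 84.9% | 97.3% | about 13% |

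In the two skewed rows almost every disagreement is a rejection by Wilcoxon alone.

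**3. Equal mean percent change, SDs 41 and 71** (common mean 64, then 13)

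| Shape | Wilcoxon rejects |
|---|---|
| Normal | 5.4%, 5.5% |
| Gamma | 7.4%, 9.8% |
| Lognormal | 9.2%, 12.2% |

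Student's t rejects in 5.2-5.7% across these settings.

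**4. Identical arms.** Each test alone stays close to 5%. Counting a trial as positive if either test is significant gives 5.8-6.6%.

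**5. Adjusting for month-3 fibrosis, same scale, 27 per arm.** Analytically, residual SD = 57.97 × sqrt(1 - r²) with 51 df:
- r = 0: SD 57.97, power 88.7%.
- |r| = 0.3: SD 57.97 × sqrt(0.91) = 55.3, power 91.4%.
- |r| = 0.5: SD 57.97 × sqrt(0.75) = 50.2, power 95.6%.

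This formula ignores chance imbalance in the covariate. Simulation with normal data includes it and comes out slightly lower:

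| abs(r) | Unadjusted t | Ordinary ANCOVA | ANCOVA with HC3 standard error |
|---|---|---|---|
| 0 | 88-89% | about 88% | 87% |
| 0.3 | 88-89% | about 90% | 89-90% |
| 0.5 | 88-89% | about 95% | 94% |

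The sign of r makes no difference. With HC3, break-even against the t-test is near |r| = 0.25. ANCOVA type I error was 4.4-5.4% across the normal and lognormal null settings.

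With lognormal data, HC3 ANCOVA has 83.1%, 85.1% and 88.9% power at |r| = 0, 0.3 and 0.5, against about 85% for the t-test and 97.3% for Wilcoxon.

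**The case against.** Three objections carry weight.

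**The open choice does little harm as a pure error rate.** Most statisticians would read the sentence as a switch to Wilcoxon when normality fails. A Shapiro-Wilk gate with identical arms gives 4.8-5.0% type I error, which is no inflation, and even deliberate selection reaches only about 6%. This stands as a limit on the size of the problem. It does not supply the missing rule, and it does not answer the point that the two tests address different quantities when spreads differ.

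**Adjustment is a preference.** An unadjusted comparison of percent change between randomized arms is valid, and the gain depends wholly on an unknown r. This also stands. Adjustment is a cheap improvement, and naming the t-test alone would close the open choice.

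**Putting Wilcoxon second gives up power if the data are skewed.** That is true: with lognormal data the gap is 97% against about 83-90%. The reason to accept it is that the trial was powered on mean percent change, and Wilcoxon does not test that.

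A reader might also infer more than the documents support:
- That month-3 fibrosis is used purely as a divisor. The conditional adjustment sentence speaks of groups, the plan's word for the arms as well, so an imbalance might bring it in as a covariate. What can be said is that no such adjustment is committed to.
- That the 9% and 13% disagreement rates are false positives. They arise under a true planned effect and are mostly extra Wilcoxon power.
- That Wilcoxon could reject in about 20% of trials with equal means. That needs an SD of 103% in one arm, which is not in the plan.
- That the trial is underpowered. On its own inputs it is not.

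**Conclusion.** The concern holds in a limited form. The plan does not fix the test for its primary fibrosis comparison, and its one adjustment sentence is data-triggered, unspecific and of unclear scope. The practical risk is an ambiguous result on the primary endpoint, together with a Wilcoxon rejection rate of up to 9-12% when mean percent change is equal. That upper range requires lognormal data and SDs of 41 and 71; with normal data the rate is about 5%. The possible benefit from adjustment runs from a loss of 1-2 points of power at r = 0 to a gain of about 5-6 points at |r| = 0.5.

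This should be corrected, but it does not invalidate the design. Confidence is medium: the gap in the text is plain, while the sizes rest on assumed shapes and an unknown correlation.

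**What to change.** Before the data are seen, state in the Statistical analysis section that:
- the primary analysis is ANCOVA of percent change in interstitial fibrosis (month 3 to month 12) on arm and month-3 fibrosis, reported as the adjusted difference in means with a 95% CI;
- any use of a heteroscedasticity-robust standard error is decided now (it is optional);
- Wilcoxon is a sensitivity analysis that cannot replace the primary result;
- the baseline-significance trigger does not apply to the arm comparison.

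If the team does not expect month-3 fibrosis to predict change, naming the t-test as the single primary analysis still closes the open choice. A log-scale ANCOVA should be secondary at most, because it compares geometric means and so changes the quantity estimated.

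The cost is a few sentences, with no new patients or biopsies and no change of outcome. The statistical price is up to about 1 point of power (ordinary ANCOVA) or 2 points (HC3) if r = 0, and less power than Wilcoxon if the data are strongly skewed. Percent change is undefined for a zero month-3 reading, but that is already so under the current plan. The 89% power statement needs no change.

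### The fibrosis comparison names no unequal-variance test, although the plan's own SDs are 41 and 71; pre-specifying Welch is a cheap, modest improvement

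*Combined protocol and SAP*

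**What the plan says.** All of this stands in the Statistical analysis section and its paragraph on sample size and power.

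- **Test.** For percent change in fibrosis and for eGFR: "Student's T-test or comparable non-parametric tests (such as the Wilcoxon Rank Sum test) will be used to compare the groups for these continuous variables". Neither a pooled nor an unequal-variance form is specified, and no rule decides between the t-test and the rank test.
- **Planning values.** Percent change in fibrosis is taken as mean 64, SD 41 in the control arm and mean 13, SD 71 in the investigational arm.
- **Numbers.** "A total of 60 patients, 30 *randomized* in each arm". With 10% loss in each arm, "27 patients in each group will have baseline and follow-up biopsies".
- **Power.** This design "will provide 89% power (alpha=0.05, two-sided").
- **Missing biopsies.** The intent-to-treat principle gives way where no 12-month biopsy is available, so such patients leave this comparison.

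**The concern.** Student's t-test, read in the usual way, estimates one common SD for both arms. The plan's own SDs differ by a factor of 71/41 = 1.73. Equal arm sizes nearly cancel the effect of pooling; unequal sizes do not. The evaluable numbers depend on who has a 12-month biopsy, the trial is open label, and only one arm changes drugs, so equal loss cannot be taken for granted.

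At stake is the calibration of the main p-value and confidence interval. If the arm with the larger SD ends up smaller, the pooled standard error is too small: the test rejects too often and the interval is too narrow. If the control arm ends up smaller, the reverse happens.

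**Working it through.** **Inputs.** From the sample size paragraph: means 64 and 13, SDs 41 and 71, 27 evaluable per arm, two-sided alpha 0.05. Assumed, because the documents give no unequal split: the splits in the table below, and SDs that stay at 41 and 71 when the means are equal.

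**1. The plan's power.**

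- Difference: 64 − 13 = 51.
- Common SD: √((41² + 71²)/2) = √3361 = 57.97.
- Standard error at 27/27: 57.97 × √(2/27) = 15.78.
- Noncentrality: 51/15.78 = 3.23.
- Noncentral t with 52 df: power 88.7%. The stated 89% reproduces.
- Welch at the same sizes (41.6 df): 88.4% by formula, 88.5% by simulation.

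**2. Why unequal sizes matter.** With n₁ control and n₂ investigational patients, the true variance of the difference in means is 41²/n₁ + 71²/n₂. The pooled test on average uses s²(1/n₁ + 1/n₂), where s² = [(n₁−1)41² + (n₂−1)71²]/(n₁+n₂−2).

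- 27/27: true 248.96, pooled 248.96, ratio 1.00.
- 30/24: true 56.03 + 210.04 = 266.07. Pooled s² = (29×1681 + 23×5041)/52 = 3167.2, times 0.075 = 237.54. Ratio 1.12, so the pooled standard error is too small by a factor of √1.12 = 1.06.
- 24/30: true 70.04 + 168.03 = 238.07. Pooled s² = (23×1681 + 29×5041)/52 = 3554.8, times 0.075 = 266.61. Ratio 0.89, so the pooled standard error is too large.

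**3. Type I error at nominal 5%.** Simulated normal data with equal means and SDs 41/71. A dash means the figure is not reported here.

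| Control/investigational | Pooled t | Rank-sum | Welch |
|---|---|---|---|
| 27/27 | 5.1% | 5.3% | 5.0% |
| 28/26 | 5.6% | 5.7% | 5.0% |
| 29/25 | 6.0% | 6.0% | 5.0% |
| 30/24 | 6.5% | 6.1% | 5.0% |
| 28/20 | 7.4% | – | 5.0% |
| 30/20 | 7.7% | 6.9% | 5.0% |
| 24/30 | 3.9% | 4.6% | 5.0% |
| 20/30 | 3.2% | 4.0% | 5.0% |

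The last digit varies between simulation runs by about 0.1 to 0.2 points. With equal SDs in both arms, the pooled test stays at about 5.0% at every split tried.

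**4. Interval coverage under the plan's own alternative** (means 64 and 13, SDs 41 and 71). The pooled 95% interval covers the true difference 93.6% of the time at 30/24, 92.3% at 30/20 and 96.9% at 20/30. The Welch interval covers 95.0–95.1%.

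**5. Power at unequal splits.** At 30/24, Welch has 86.0% and the pooled test 88.9%, the latter at an inflated error rate. At 24/30, Welch has 89.9% and the pooled test 87.8%.

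**The case against.** A reader might infer that the plan fixes a pooled-variance t-test as the primary test and that its error leaves 5% whenever biopsies are lost unequally. The documents do not support that, for four reasons.

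- **The test is not fixed.** The text also allows a rank test and never mentions pooling. This stands: the pooled form is only the conventional reading of the name. The alternative it offers is not a remedy, since the rank-sum test also drifts under unequal spread.
- **The SDs are planning values under the alternative.** They go with means of 64 and 13. If treatment does nothing at all, both arms share one distribution, and both named tests hold their level. This stands, and it limits the type I figures to a null of equal means with unequal spread. It does not remove the coverage problem, which arises under the plan's own expected result.
- **The unequal splits are not in the plan.** It expects 27/27, where the problem is negligible. If each arm lost 10% by chance alone, the investigational arm would lose at least 4 more biopsies than control in about 6% of trials, and at least 6 more in about 0.9%. A split of 28/20 means that 12 of 60 are lost overall, twice the planned rate. This stands: large imbalance needs truly differential loss, whose size is unknown.
- **Welch is exact for neither small nor skewed samples.** Percent change in fibrosis cannot fall below −100, yet a normal distribution with mean 13 and SD 71 puts 5.6% of patients there. With a lognormal ratio (assumed; both means 13, SDs 41/71), Welch runs at 5.5% at 27/27, 5.9% at 30/24 and 6.2% at 28/20, against 5.6%, 6.9% and 7.7% for the pooled test. This stands: Welch is still better, by less than the normal-data table shows.

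**Conclusion.** The point holds as a cheap improvement of modest size. The named method sits badly with the plan's own SDs, and nothing in the text directs the analyst to an unequal-variance version. With the planned equal loss the consequence is negligible. With imbalances of 2 to 6 evaluable patients against the investigational arm, the pooled test runs at about 5.6% to 6.5%. It passes 7% only at about 8 or more, and it is conservative when the control arm loses more.

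These figures assume normal data, SDs that stay at 41 and 71 when the means are equal, and splits that the documents do not give. A reader might also infer that the 89% power is wrong. It is not: it reproduces for the pooled test at 27 per arm.

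**What to change.** In the Statistical analysis section, name the unequal-variance (Welch) t-test and its 95% confidence interval for the comparison of percent change in fibrosis. If a regression is used instead, name heteroscedasticity-robust (HC3) standard errors. In the sample size paragraph, give the power as 88% at 27 per arm for that test.

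The cost is a few words and no patients. Power falls by about 0.2 to 0.3 points at 27/27 (88.4–88.5% against 88.7%). It would be about 86% at 30/24, which should be stated as the price if the investigational arm loses more biopsies.
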